Appendix 2 Outcome Assessment Tools

List of the outcome assessment tools:

National Institutes of Health Chronic Prostatitis Symptom Index (NIH-CPSI)

International Prostate Symptom Score (IPSS)

Hospital Anxiety and Depression Scale (HADS)

International Index of Erectile Function 5 (IIEF-5)

European Quality of Life-5 Dimensions-5 Levels (EQ-5D-5L)

Expectation Assessment

National Institutes of Health Chronic Prostatitis Symptom Index (NIH-CPSI)

Pain or Discomfort		Yes	No	6. How often have you had to urinate again less than two hours after you finished urinating, over the last week?	
1. In the last week, have you experienced any pain or discomfort in the following areas?				 0 Not at all  1 Less than 1 time in 5  2 Less than half the time  3 About half the time  4 More than half the time  5 Almost always	
a. Area between rectum and testicles (perineum)		 1	 0		
b. Testicles		 1	 0		
c. Tip of the penis (not related to urination)		 1	 0		
d. Below your waist, in your pubic or bladder area		 1	 0		
2. In the last week, have you experienced:		Yes	No	Impact of Symptoms	
a. Pain or burning during urination?		 1	 0	7. How much have your symptoms kept you from doing the kinds of things you would usually do, over the last week?	
b. Pain or discomfort during or after sexual climax (ejaculation)?		 1	 0	 0 None  1 Only a little  2 Some  3 A lot	
3. How often have you had pain or discomfort in any of these areas over the last week?				8. How much did you think about your symptoms, over the last week?	
 0 Never  1 Rarely  2 Sometimes  3 Often  4 Usually  5 Always				 0 None  1 Only a little  2 Some  3 A lot	
4. Which number best describes your AVERAGE pain or discomfort on the days that you had it, over the last week?				Quality of Life	
				9. If you were to spend the rest of your life with your symptoms just the way they have been during the last week, how would you feel about that?	
0 NO PAIN		10 PAIN AS		 0 Delighted  1 Pleased  2 Mostly satisfied  3 Mixed (about equally satisfied and dissatisfied)  4 Mostly dissatisfied  5 Unhappy  6 Terrible	
BAD AS		YOU CAN			
IMAGING					
Urination					
5. How often have you had a sensation of not emptying your bladder completely after you finished urinating, over the last week?					
 0 Not at all  1 Less than 1 time in 5  2 Less than half the time  3 About half the time  4 More than half the time  5 Almost always					
Scoring the NIH-Chronic Prostatitis Symptom Index Domains					
Pain: Total of items 1a, 1b, 1c, 1d, 2a, 2b, 3, and 4 = _____					
Urinary Symptoms: Total of items 5 and 6 = _____					
Quality of Life Impact: Total of items 7, 8 and 9 = _____					

International Prostate Symptom Score (IPSS)

	Not at all	Less than 1 time in 5	Less than half the time	About half the time	More than half the time	Almost always	Your score
Incomplete emptying Over the past month, how often have you had a sensation of not emptying your bladder completely after you finish urinating?	0	1	2	3	4	5	
Frequency Over the past month, how often have you had to urinate again less than two hours after you finished urinating?	0	1	2	3	4	5	
Intermittency Over the past month, how often have you found you stopped and started again several times when you urinated?	0	1	2	3	4	5	
Urgency Over the last month, how difficult have you found it to postpone urination?	0	1	2	3	4	5	
Weak stream Over the past month, how often have you had a weak urinary stream?	0	1	2	3	4	5	
Straining Over the past month, how often have you had to push or strain to begin urination?	0	1	2	3	4	5	
	None	1 time	2 times	3 times	4 times	5 times	
Nocturia Over the past month, many times did you most typically get up to urinate from the time you went to bed until the time you got up in the morning?	0	1	2	3	4	5	

Hospital Anxiety and Depression Scale (HADS)

Tick the box beside the reply that is closest to how you have been feeling in the past week. Don't take too long over your replies: your immediate is best.

1. I feel tense or 'wound up':	8. I feel as if I am slowed down:
3 Most of the time	3 Nearly all the time
2 A lot of the time	2 Very often
1 From time to time, occasionally	1 Sometimes
0 Not at all	0 Not at all
2. I still enjoy the things I used to enjoy:	9. I get a sort of frightened feeling like 'butterflies' in the stomach:
 0 Definitely as much	 0 Not at all
 1 Not quite so much	 1 Occasionally
 2 Only a little	 2 Quite Often
 3 Hardly at all	 3 Very Often
3. I get a sort of frightened feeling as if something awful is about to happen:	10. I have lost interest in my appearance:
 3 Very definitely and quite badly	 3 Definitely
 2 Yes, but not too badly	 2 I don't take as much care as I should
 1 A little, but it doesn't worry me	 1 I may not take quite as much care
 0 Not at all	 0 I take just as much care as ever
4. I can laugh and see the funny side of things:	11. I feel restless as I have to be on the move:
 0 As much as I always could	 3 Very much indeed
 1 Not quite so much now	 2 Quite a lot
 2 Definitely not so much now	 1 Not very much
 3 Not at all	 0 Not at all
5. Worrying thoughts go through my mind:	12. I look forward with enjoyment to things:
 3 A great deal of the time	 0 As much as I ever did
 2 A lot of the time	 1 Rather less than I used to
 1 From time to time, but not too often	 2 Definitely less than I used to
 0 Only occasionally	 3 Hardly at all
6. I feel cheerful:	13. I get sudden feelings of panic:
 3 Not at all	 3 Very often indeed
 2 Not often	 2 Quite often
 1 Sometimes	 1 Not very often
 0 Most of the time	 0 Not at all
7. I can sit at ease and feel relaxed:	14. I can enjoy a good book or radio or TV program:
 0 Definitely	 0 Often
 1 Usually	 1 Sometimes
 2 Not Often	 2 Not often
 3 Not at all	 3 Very seldom

International Index of Erectile Function 5 (IIEF-5)

1. How do you rate your confidence that you could get and keep an erection?	 ₀ No confidence  ₁ Very low  ₂ Low  ₃ Moderate  ₄ High  ₅ Very high
2. When you had erections with sexual stimulation, how often were your erections hard enough for penetration?	 ₀ No sexual activity  ₁ Almost never/never  ₂ A few times (much less than half the time)  ₃ Sometimes (about half the time)  ₄ Most times (much more than half the time)  ₅ Almost always/always
3. During sexual intercourse, how often were you able to maintain your erection after you had penetrated (entered) your partner?	 ₀ No sexual intercourse  ₁ Almost never/never  ₂ A few times (much less than half the time)  ₃ Sometimes (about half the time)  ₄ Most times (much more than half the time)  ₅ Almost always/always
4. During sexual intercourse, how difficult was it to maintain your erection to completion of intercourse?	 ₀ No sexual intercourse  ₁ Extremely difficult  ₂ Very difficult  ₃ Difficult  ₄ Slightly difficult  ₅ Not difficult
5. When you attempted sexual intercourse, how often was it satisfactory for you?	 ₀ No sexual intercourse  ₁ Very low  ₂ Low  ₃ Moderate  ₄ High  ₅ Very high

European Quality of Life-5 Dimensions-5 Levels (EQ-5D-5L)

MOBILITY	
I have no problems in walking about	
I have slight problems in walking about	
I have moderate problems in walking about	
I have severe problems in walking about	
I am unable to walk about	
SELF-CARE	
I have no problems washing or dressing myself	
I have slight problems washing or dressing myself	
I have moderate problems washing or dressing myself	
I have severe problems washing or dressing myself	
I am unable to wash or dress myself	
USUAL ACTIVITIES (e.g. work, study, housework, family or leisure activities)	
I have no problems doing my usual activities	
I have slight problems doing my usual activities	
I have moderate problems doing my usual activities	
I have severe problems doing my usual activities	
I am unable to do my usual activities	
PAIN/DISCOMFORT	
I have no pain or discomfort	
I have slight pain or discomfort	
I have moderate pain or discomfort	
I have severe pain or discomfort	
I am extreme pain or discomfort	
ANXIETY/DEPRESSION	
I am not anxious or depressed	
I am slightly anxious or depressed	
I am moderately anxious or depressed	
I am severely anxious or depressed	
I am extreme anxious or depressed	

Expectation Assessment

In general, is acupuncture effective for controlling the illness?
 Yes
 No
 Unclear
Do you think acupuncture will be helpful to improve your CP/CPPS symptoms
 Yes
 No
 Unclear

Common symptoms of CP/CPPS include discomfort in the perineum, suprapubic region, and lower urinary tract symptoms⁶. Patients with CP/CPPS also frequently experience a wide array of sexual dysfunctions, including erectile dysfunction (ED), painful ejaculation and premature ejaculation (PE)^{7–11}, on top of symptoms suggestive of negative cognition or emotional consequences¹². The aforementioned symptoms negatively impact upon the patient's quality of life (QoL) to a similar degree or worse than those of congestive heart failure, Crohn's disease, diabetes mellitus or angina^{13, 14}. Because of its high prevalence and lack of effective therapies, direct and indirect costs associated with CP/CPPS are substantial¹⁵. Approximately 25% of men experience loss of work and approximately 50% have reduced leisure time at some point due to CP/CPPS¹⁶. The direct and indirect cost of care in China approaches 8059 CNY per person in 2009¹⁷, and data indicate that in the USA, the total annual cost for patients with prostatitis was US\$4387 in 2006¹⁵.

Unlike acute/chronic bacterial prostatitis, the cause of CP/CPPS is unknown and no well-conducted epidemiologic studies are available to support any particular risk factors¹⁸. The diagnosis of CP/CPPS is mainly based on symptoms. Treatments for CP/CPPS usually include alpha-blockers, antibiotics, nonsteroidal anti-inflammatory drugs (NSAIDs), and phytotherapy. Alpha-blockers and antibiotics have moderate effects on pain, voiding and QoL¹⁹. Both alpha-blockers and antibiotics are recommended for patients with CP/CPPS for less than 1 year, but only antibiotics are recommended in treatment-naïve patients. NSAIDs and phytotherapy are less commonly used, because of lack of research evidence¹⁹. Although advances have been made in research and developing novel treatment options, definitive treatments for CP/CPPS are still lacking¹⁹. Besides, pharmacological interventions are accompanied with adverse effects such as dizziness, nausea, and postural hypotension, which also reduce patients' compliance to treatments²⁰. Previous studies suggest that acupuncture may be a potential treatment for CP/CPPS^{21–25}. However, owing to small sample sizes and other methodological limitations of clinical trials, the efficacy of acupuncture in CP/CPPS remains inconclusive^{19, 26}. In addition, the durable efficacy of the acupuncture is still unclear.²⁷

NIH consensus classification of prostatitis	Definition
(I) Acute bacterial prostatitis	Acute infection of the prostate
(II) Chronic bacterial prostatitis	Chronic or recurrent infection of the prostate
(III) Chronic prostatitis/chronic pelvic pain syndrome	No demonstrated infection
A. Inflammatory	Leukocytes in expressed prostatic secretions, post prostate massage urine, or semen
B. Noninflammatory	No evidence of inflammation
(IV) Asymptomatic inflammatory prostatitis	No subjective symptoms detected, inflammation shown either by prostate biopsy or the presence of leukocytes in EPS/semen during evaluation for infertility or other disorders

Table 1. NIH consensus classification and definition of 4 categories of prostatitis¹

2. Study Objective

The objective of this multi-center, randomized, sham acupuncture-controlled trial is to assess the effectiveness, especially the long-term efficacy of acupuncture for relieving symptoms of CP/CPGS.

3. Design

3.1 Overview

This is a multicenter, participants-blinded, parallel-group, randomized controlled study conducted in China.

The participants will be recruited in 10 clinical sites, which are Dongfang Hospital Beijing University of Chinese Medicine; Beijing Fengtai Hospital of Integrated Traditional and Western Medicine; West China Hospital of Sichuan University; The Third Affiliated Hospital of Zhejiang Chinese Medical University; The First Affiliated Hospital of Anhui University of Chinese Medicine; Hengyang Hospital Affiliated to Hunan University of Chinese Medicine; The First Hospital of Hunan University of Chinese Medicine; Guangdong Provincial Hospital of Traditional Chinese Medicine; Yantai Hospital of Traditional Chinese Medicine; and Shaanxi Provincial Hospital of Traditional Chinese Medicine. Guang'anmen Hospital, China Academy of Chinese Medical Sciences will be responsible for study design and organization. A data coordination center will be established at China Academy of Chinese Medical Sciences (CACMS) to monitor data management.

3.2 Eligibility criteria

3.2.1 Inclusion Criteria

- (1) History of pain perceived in the prostate region and absence of other lower urinary tract pathology for a minimum of three of the past 6 months. In addition, any associated lower urinary tract symptoms, sexual function, and psychological factors should be addressed. Physical examinations, urinary analyses, and urine cultures will be performed for all subjects;
- (2) Age 18 to 50 years;
- (3) NIH-CPSI total score ≥ 15 .

3.2.2 Exclusion criteria

- (1) Other types of prostatitis, such as acute bacterial prostatitis, chronic bacterial prostatitis, or asymptomatic inflammatory prostatitis;
- (2) Urinary tract infection with a urine culture value $>100,000$ colony forming units (CFU)/mL, clinical evidence of urethritis, including urethral discharge or positive culture, diagnostic of sexually transmitted diseases (including gonorrhoea, chlamydia, mycoplasma or trichomonas, but not including HIV/AIDS), symptoms of acute or chronic epididymitis;
- (3) Prostate, penile, testicular, bladder, or urethral cancer, seizure disorder in any medical history;
- (4) Inflammatory bowel disease, active urethral stricture, bladder outlet obstruction, neurologic disease or disorder affecting the bladder, neurologic impairment or psychiatric disorder preventing understanding of consent and self-report scale;
- (5) Overactive bladder, neurogenic bladder, interstitial cystitis, glandular cystitis;
- (6) Organic disease of the urinary system;
- (7) Severe cardiac, lung, cerebrum, liver or renal system disease, or hematopoietic system disease;
- (8) Residual urine volume ≥ 100 mL;
- (9) Qmax ≤ 15 mL/s;
- (10) During previous 4 weeks prior to study participation, used androgen hormone inhibitors (finasteride), alpha-blockers (terazosin, doxazosin mesylate, tamsulosin hydrochloride), antibiotics

(ciprofloxacin hydrochloride), or any other prostatitis-specific medication (including herbal and Chinese medicine)

4. Schedule of Evaluation

	STUDY PERIOD											
	Enrolment	Allocation	Treatment								Follow-up	
TIMEPOINT (W, week)	-2 and -1	0	1	2	3	4	5	6	7	8	20	32
Enrolment												
Informed consent	x											
Eligibility criteria	x											
Demography characteristics	x											
Allocation		x										
Interventions												
Acupuncture			x	x	x	x	x	x	x	x		
Sham acupuncture			x	x	x	x	x	x	x	x		
Assessments												
Proportion of responders										x		x
NIH-CPSI	x		x	x	x	x	x	x	x	x	x	x
IPSS	x					x				x	x	x
IIEF-5	x									x	x	x
HADS	x									x	x	x
EQ-5D-5L	x									x	x	x
GRA					x				x	x	x	
Expectation assessment	x											
Urinary flow rate	x								x		x	

Table 2. Enrolment, Intervention and Evaluation Schedules

Abbreviations: NIH-CPSI National Institutes of Health Chronic Prostatitis Symptom Index, IIEF-5 International Index of Erectile Function 5, HADS Hospital Anxiety and Depression Scale, GRA Global Response Assessment, EQ-5D-5L Five-level EuroQol five-dimensional questionnaire, VAS visual analogue scale

5. Efficacy and Safety outcomes

5.1 Efficacy outcomes

5.1.1 Primary Outcomes

The two co-primary outcomes include the proportions of responders at week 8 and week 32. The responder is defined as a participant with a decline of 6 points or more from baseline in the total score of the Chinese version NIH-CPSI. As a validated, self-reported questionnaire, NIH-CPSI is widely used to assess CP/CPPS symptoms^{28, 29}. NIH-CPSI consists of 9 items divided into 3 discrete domains: pain (0–21 points), urinary symptoms (0–10 points) and QoL (0–12 points), with a total score of 0–43 points (a higher score indicates worse symptoms). A decline of at least 6 points in NIH-CPSI has been identified as the minimal clinically important difference (MCID)²⁵.

5.1.2 Secondary Outcomes

(1) Proportion of responders during weeks 1–7, and at week 20.

The NIH-CPSI will be assessed once a week during treatment, and at week 20 and week 32. The responder is defined as who has a decline of 6 or more than 6-point from baseline measured by using the NIH-CPSI.

(2) The change from baseline in NIH-CPSI total score during weeks 1–8, at week 20, and at week 32.

(3) The change from baseline in NIH-CPSI subscales (pain, urinary symptoms and QoL) during weeks 1–8, at week 20, and at week 32.

(4) The change from baseline in IPSS at week 4, week 8, week 20, and week 32.

IPSS is a valid, reliable and sensitive measure for patients with lower urinary tract symptoms (LUTS); it is widely used in clinical practice and research to determine the severity of LUTS, including incomplete bladder emptying, frequency of urination, intermittency, urgency, weak urine stream, straining and nocturia^{30, 31}. Each of the questions is rated from 0 (not at all) to 5 (almost always); severity of LUTS can be graded as mild (0–7), moderate (8–19) or severe (20–35). IPSS will be assessed at the end of the 4th, 8th, 20th, and 32nd week.

(5) The change from baseline in HADS at week 8, week 20, and week 32.

HADS will be assessed at the end of the week 8, week 20, and week 32. HADS is made up of 7 items for the assessment of depression and anxiety; the completion of this scale usually requires 2–5 minutes³².

(6) The change from baseline in IIEF-5 at week 8, week 20, and week 32.

Chinese version IIEF-5 will be assessed at the end of the week 8, week 20, and week 32. The IIEF-5 consists of 15 items in 5 domains with a total score ranging from 5 to 25 (mild ED, 12–21; moderate ED, 8–11; severe ED, 5–7); it is a psychometrically valid and reliable instrument with high sensitivity and specificity for detecting treatment effects in patients with ED of a broad spectrum of aetiology³³.

(7) The change from baseline in EQ-5D-5L at week 8, week 20, and week 32.

The EQ-5D-5L will be assessed at the end of week 8, week 20, and week 32. The EQ-5D-5L is a generic instrument designed for self-completion and postal surveys; it is well-established and suitable for evaluation of QoL in participants with CP/CPPS³⁴.

(8) The proportions of participants in each response category of the Global Response Assessment (GRA) at week 4, week 8, week 20, and week 32.

The proportions of participants in each response category of the GRA in the two groups after treatment will be measured at the end of the week 4, week 8, week 20, and week 32. GRA consists of 7 response categories: markedly worsened, moderately worsened, slightly worsened, no change, slightly improved,

moderately improved, and markedly improved. We will identify a participant who reports “moderate” or “marked improvement” as a responder³⁵.

(9) The change for peak and average urinary flow rates from baseline at weeks 8 and 32.

Peak and average urinary flow rates will be measured at weeks 8 and 32.

(10) Expectation assessment at baseline

Expectation assessment will be assessed at baseline, which includes two brief questions to investigate whether patients are confident that acupuncture treatment will help their CP/CPPS: “In general, is acupuncture effective for controlling the illness?”, “Do you think acupuncture will be helpful to improve your CP/CPPS symptoms?” For each question, participants could choose “Yes”, “No” or “Unclear” as the answer.

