11.1 Sample Size Calculations

Sample-size calculations were based on 90% power to detect a difference of 17% between response rates in the two groups (63.7% in the acupuncture group compared with 46.7% in the control group) for the primary outcome, defined as a decline of 6 or more points in the NIH-CPSI total score²¹. These values are equivalent to an odds ratio of 2.0. On the basis of a two-sided alpha level of 0.05, we calculated that a sample of 440 participants will be required (220 in each group). This proposed sample size includes a 15% increase to account for dropouts. To control for type I error, the two time points in the primary outcomes will have to be positive in order for the trial to prove the efficacy of acupuncture.

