6.3.2 Demographics and Baseline Characteristics

All data recorded at baseline will be summarized by group. Comparisons between groups will be performed using the methodology described in section 6.3.1. Summaries will be presented for the ITT Set in both groups.

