6.3.3 Analyses for Primary Outcome

Primary outcome analysis will be conducted with a logistic generalized linear mixed model (GLMM) for repeated measures. Responder or non-responder at each scheduled post-baseline visit (end of treatment, and 20 and 24 weeks after treatment) is the dependent variable. Subjects who discontinue without providing the NIH-CPSI score will be considered as non-responders. The logistic GLMM is fitted using the logit link and the binomial distribution. The model will include the baseline NIH-CPSI total score as a fixed-effect covariate, with treatment group (acupuncture and sham acupuncture), visit and treatment \times visit interaction as fixed-effect categorical factors. The interaction will remain in the model regardless of significance. Treatment group comparisons at each visit will be estimated by differences between least squares means from the treatment \times visit interaction, and will be presented as odds ratios with accompanying *p* values and 95% CIs. The predicted probability of response at each visit will also be presented. Such models provide fairly robust results for treatment comparisons when longitudinal binary responses are missing, with an assumption that data are missing at random(MAR), according to reported values³⁶.

Sensitivity Analyses for the Primary Outcome

Because the MAR assumption cannot be verified using the data, the sensitivity of inferences to departures from the MAR assumption should be tested³⁷. A straightforward sensitivity analysis for the MAR assumption in multiple imputation is based on the control-based pattern imputation model under the MNAR assumption by using the SAS procedure Proc MI process. Therefore, mixed-effect model under MNAR assumption will be used. 6.3.4 Analyses for Secondary Outcome

Efficacy analyses for all secondary outcomes will be performed in the ITT population, without imputation of missing data.

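### Treatment expectation, measured only before randomisation, is listed as a secondary efficacy outcome and so falls under the plan's between-group efficacy comparisons

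*Combined protocol and SAP*

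**What the plan says.** Protocol 5.2 puts the expectation assessment among the questionnaires that men complete at home at the end of screening. These are collected at Visit 2, and protocol 5.3 places randomisation at that visit. The evaluation schedule (Table 2 in both documents) marks expectation only in the column for weeks -2 and -1.

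Item (10) of the secondary outcomes nevertheless reads: "Expectation assessment will be assessed at baseline, which includes two brief questions". In the SAP this item stands in 5.1.2, within section 5.1 on efficacy outcomes. Protocol 8.1.2 has the same item.

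Three SAP rules then apply:

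- 6.3.4 says: "Efficacy analyses for all secondary outcomes will be performed in the ITT population, without imputation of missing data". It also sends remaining categorical or ordinal data to a Wilcoxon, chi-square or Fisher test between groups.
- 6.3.1 promises a treatment difference with a two-sided 95% interval for primary and secondary outcomes, tests at 5%, and does not adjust secondary outcomes for multiplicity.
- 6.3.2, on baseline data, says: "Comparisons between groups will be performed using the methodology described in section 6.3.1".

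Expectation enters no model. For the primary responder model, "The model will include the baseline NIH-CPSI total score as a fixed-effect covariate", alongside treatment, visit and their interaction. The linear mixed model for change in NIH-CPSI has the same structure.

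**The concern.** An efficacy outcome has to be something that treatment could change. These two questions are answered before allocation, so the groups differ only by the chance of randomisation and the null hypothesis of a between-group test is true by design. A significant result would say nothing about acupuncture, yet it would stand in the secondary efficacy results. The same variable also qualifies as baseline data under 6.3.2, so the SAP handles it in two ways.

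A second, smaller question is whether the answers should be used as a covariate. The endpoint is self-reported and the control is a sham needling procedure, so expectation is a plausible predictor of response. The documents give no figure for how strong a predictor it is.

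**Working it through.** **1. Timing against classification.** Questionnaires completed in screening (protocol 5.2), collected at Visit 2, randomisation at Visit 2 (5.3), schedule mark at weeks -2 and -1 only. Against this: secondary outcome (10) in protocol 8.1.2 and SAP 5.1.2. The two cannot both be right. A variable fixed before allocation is a baseline characteristic.

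**2. Chance of a meaningless significant result.** Each test is at 5%. For two independent tests, 1 − 0.95² = 0.0975. The two questions are closely related, so their answers are probably positively correlated. Taking the two test statistics as bivariate normal with correlation r (r is assumed), the chance of at least one significant result is 8.3% at r = 0.7 and 7.0% at r = 0.9. So 9.75% is an upper figure.

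**3. The plan's own sample size.** Protocol 11.1 plans for 90% power with assumed response rates of "63.7% in the acupuncture group compared with 46.7% in the control group", two-sided alpha 0.05, and 440 men including 15% for dropout.
- Odds ratio: (0.637/0.363)/(0.467/0.533) = 2.00, as stated.
- Two-proportion formula with continuity correction: 190 per arm.
- 190 × 1.15 gives 219 per arm (438 in total); 190/0.85 gives 224 per arm (448 in total). Both are within 3% of 440, so the figure reproduces.
- Evaluable men per arm after 15% loss: 220 × 0.85 = 187.

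**4. What a covariate could add.** Method: asymptotic Wald power of a logistic model with and without a binary expectation term (Yes versus not Yes), marginal response rates held at 63.7% and 46.7%, 187 men per arm.

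Unadjusted: log odds ratio 0.6946; standard error √[(1/(0.637 × 0.363) + 1/(0.467 × 0.533))/187] = 0.2112; z = 0.6946/0.2112 = 3.29; power = Φ(3.29 − 1.96) = 90.8% per time point.

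Adjusted, with the share answering Yes and the expectation odds ratio both assumed:

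| Expectation OR | Power, 50% Yes | Power, 70% Yes | Power, 90% Yes | Treatment OR given expectation |
|---|---|---|---|---|
| 1 | 90.8% | 90.8% | 90.8% | 2.00 |
| 1.5 | 91.0% | 91.0% | 90.9% | 2.01–2.02 |
| 2 | 91.5% | 91.4% | 91.1% | 2.02–2.04 |
| 3 | 92.5% | 92.2% | 91.4% | 2.04–2.11 |
| 4 | 93.3% | 93.0% | 91.7% | 2.06–2.18 |

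The gain is 0 to 0.7 points for an odds ratio of 1 to 2, up to 1.7 points at 3, and about 2.5 points at most at 4.

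**5. Where the gain comes from.** With 50% answering Yes, the standard error of the log odds ratio rises from 0.2112 to 0.2146 at an expectation odds ratio of 2, and to 0.2199 at 3. Power increases only because the conditional odds ratio moves further from 1: at an odds ratio of 2, z = 0.7151/0.2146 = 3.33 against 3.29.

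These calculations take one time point at a time and leave out the baseline NIH-CPSI score and the repeated measures, so the true increment may differ.

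**The case against.** The strongest reply is that this is a labelling slip. No sentence names a test for expectation, the item's own title places it at baseline, and 6.3.2 already summarises baseline data by group. It is true that the test follows from general rules and not from an explicit instruction. But 6.3.4 covers all secondary outcomes and exempts none, so the plan as written does call for the comparison.

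A second reply is that moving the item to 6.3.2 changes little, because baseline data are compared there with the same tests. This stands: relabelling alone is not enough, and 6.3.2 needs a statement that no tests are done. The same reasoning covers every other baseline variable.

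A third reply is that nothing decisive is affected. This also stands. Protocol 11.1 makes success depend on weeks 8 and 32 only.

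On the covariate, a reader might infer that leaving expectation out loses precision, biases the treatment comparison or leaves a harmful chance imbalance. The documents and the arithmetic do not support this. In the logistic model the standard error rises with adjustment. Omitting the covariate does not inflate the type I error, and chance imbalance is already allowed for in the test and the interval. The documents show no prognostic strength, and if nearly all volunteers answer Yes the gain is close to nothing. Adjustment also has costs: a rule for missing answers is needed, or men would drop out of an analysis that SAP 6.2 says includes everyone randomised.

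**Conclusion.** The classification is wrong as written and should be corrected, whether or not expectation predicts response. The consequence is limited to the secondary results: a 5% chance per question of a significant difference with no meaning for efficacy, and at most 9.75% for either of two, reached only if the answers are independent. The co-primary conclusions are not affected.

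The covariate is optional and minor. Its benefit is in power, not in the standard error of the log odds ratio. It rests wholly on an assumed prognostic strength (odds ratio 1 to 4) and an assumed 50% to 90% answering Yes. It would also make the reported odds ratio conditional on expectation, about 2.02 to 2.04 against 2.00 when the expectation odds ratio is 2.

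**What to change.** 1. Delete item (10) from the secondary outcomes in protocol 8.1.2 and SAP 5.1.2.
2. Add expectation to the baseline characteristics in SAP 6.3.2, reported as counts and percentages by group for each question. Replace the sentence on between-group comparisons there with a statement that baseline variables are summarised without significance tests.
3. Optional: in SAP 6.3.3 and 6.3.4, pre-specify the answer to the CP/CPPS-specific question (Yes versus No or Unclear) as a fixed-effect covariate. Keep missing answers as not Yes, or as a separate level, so that no randomised man is dropped. State that the odds ratio is then conditional on expectation. Protocol 11.2 has the SAP finalised before database lock and code breaking, so this choice has to be made by then.

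Items 1 and 2 cost only wording. Item 3 costs one degree of freedom, or two if missing answers form their own level. None of them needs new data.
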